**Table 3 Study SPR001-203 Baseline Specifications for Specific Variables**

Parameter	Screening	Study Week 6 (Baseline)
Patient reported outcomes (HADS, SF-36, C-SSRS)		X
Laboratory safety test (Hematology, Chemistry [includes insulin profile and lipid profile], Urinalysis, Thyroid Panel, Non-Efficacy Hormones)		X
Vital signs (includes weight profile and blood pressure profile)		X
Hirsutism (mFG score)		X
Acne (IGA score)		X
Scrotal ultrasound	X	
ECG		X
GC dose level		X

The initial scrotal ultrasound may be scheduled for any time up to the Week 4 visit and will be considered the baseline measurement for the TART endpoint.

#### **9.3.11 Change from Baseline**

Change from baseline is calculated as the post-baseline assessment subtracted by the baseline assessment.

#### **9.3.12 Percent Change from Baseline**

Percent change from baseline is calculated for the individual subject as the change from baseline divided by the baseline assessment and multiplied by 100%.

#### **9.3.13 Change from Baseline on the Log Scale**

The change from baseline on the log scale is calculated as the difference of the log (post-baseline assessment) subtracted by the log (baseline assessment). It is also mathematically equivalent to the log of the ratio of the post-baseline assessment divided by the baseline assessment.

$$\begin{aligned} \text{change from baseline on the log scale} &= \log(\text{post baseline assessment}) - \log(\text{baseline assessment}) \\ &= \log \left( \frac{\text{post baseline assessment}}{\text{baseline assessment}} \right) \end{aligned}$$

### 9.3.14 Geometric Mean Ratio and Percent Change

For efficacy variables of A4, 17-OHP, and ACTH, the geometric mean ratio (GMR) and percent change from baseline will be calculated by treatment group and dose level. The GMR is derived from the natural logarithm of the post-baseline value divided by the baseline value [ $\log(\text{post-baseline}/\text{baseline})$ ]. The GMR is the exponential function of the mean of  $\log(\text{post baseline}/\text{baseline})$ . The 95% CI of GMR is the exponential function of the 95% CI of the mean [ $\log(\text{post baseline}/\text{baseline})$ ]. The percent change is derived as  $100 \times (\text{GMR} - 1)$ . The 95% CI of percent change is  $100 \times (95\% \text{ CI of GMR} - 1)$ .

### 9.3.15 Upper Limit of Normal or Target by Efficacy Biomarker

The ULN and Target values that are displayed in [Table 4](#) will be used in data analysis. The age at screening will be used to determine those age specific ULN values.

The following table lists the pre-specified, Sponsor-provided upper limit of normal values.

**Table 4 Upper Limit of Normal Values by Subgroup and Key Biomarker**

Baseline Characteristic	ACTH ULN	17-OHP ULN	17-OHP Target	A4 ULN
Males: 18-30	63.3 ng/dL	200 ng/dL	1200 ng/dL	220 ng/dL
Males: 31-50	63.3 ng/dL	200 ng/dL	1200 ng/dL	190 ng/dL
Males: 51+	63.3 ng/dL	200 ng/dL	1200 ng/dL	220 ng/dL
Females: pre-menopausal	63.3 ng/dL	200 ng/dL	1200 ng/dL	285 ng/dL
Females: post-menopausal	63.3 ng/dL	200 ng/dL	1200 ng/dL	75 ng/dL

### 9.3.16 Responder Definitions

The exploratory variables are proportions of responders based on each of the serum hormone assessments and GC. Indicator variables will be created for each of the three responder criteria as depicted in [Table 5](#). Missing assessments are counted as non-responders.

**Table 5 Responder Definition by Endpoint**

Endpoint	Definition
Proportion of subjects who achieve $A4 \leq x^1 \times ULN$ after 12 weeks on treatment (Week 18)	$\begin{cases} 1 & A4 \leq x \times ULN \\ 0 & A4 > x \times ULN \text{ OR missing} \end{cases}$
Proportion of subjects who achieve $17-OHP \leq 1200 \text{ ng/dL}$ after 12 weeks on treatment (Week 18)	$\begin{cases} 1 & 17-OHP \leq 1200 \text{ ng/dL} \\ 0 & 17-OHP > 1200 \text{ ng/dL OR missing} \end{cases}$
Proportion of subjects with at least a 5 mg/day HCe reduction from baseline in GC dose and $A4 \leq ULN$	$\begin{cases} 1 & \Delta GC \text{ dose} \leq -5 \text{ mg/day in HCe AND } A4 \leq ULN \\ 0 & \Delta GC \text{ dose} > -5 \text{ mg/day OR } A4 > ULN \text{ OR missing} \end{cases}$

 =  $x = 1, 1.25, 1.5, 1.75$  and 2.

### 9.3.17 HADS Total Score

The scale consists of 14 items, 7 items each for anxiety and depression. The anxiety score is the sum of the odd-numbered items (questions 1, 3, 5, 7, 9, 11, 13), and the depression score is the sum of the even-numbered items (questions 2, 4, 6, 8, 10, 12, 14).

Each item is rated on a 4-point scale based on the frequency of symptoms over the preceding week and ranging from 0 (not at all) to 3 (very often). The sub-scores are the sum of individual item scores within each subcategory (anxiety or depression) and ranges from 0 to 21, with higher scores corresponding to higher levels of anxiety or depression. The total score of the individual item scores and ranges from 0 to 42, with higher scores corresponding to higher levels of anxiety or depression.

### 9.3.18 SF-36 Total Score

The SF-36 consists of 36 items in the following 8 domains: physical functioning, physical role functioning (limitations in usual role activities because of physical health problems), bodily pain, general health perceptions, vitality, social functioning, emotional role functioning (limitations in usual role activities because of emotional problems), and mental health. Domain scores range from 0 to 100, with higher scores corresponding to better subjective health status.

The SF-36 total score and 8 domain scores will be computed by the CRO providing the clinical trial database and provided, analysis ready, in relevant output datasets.

#### **9.3.19 Modified Ferriman-Gallwey Total Score**

The mFG scores each of 9 body areas on a scale of 0 (no hair) to 4 (hairiness typical of a man), with the sum of the separate scores providing a hormonal hirsutism score.

The total score is the sum of the individual item scores and ranges from 0 to 36, with higher scores corresponding to body hair patterns more typical of a man.

A subject with hirsutism at baseline is defined as an mFG score of 8 or more.

#### **9.3.20 Homeostatic Model Assessment of Insulin Resistance**

HOMA-IR is calculated using the following equations:

$$HOMA-IR = \frac{\text{glucose (mg/L)} * \text{insulin(mIU/L)}}{405} \text{ or } \frac{\text{glucose (mmol/L)} * \text{insulin(mIU/L)}}{22.5}$$

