8.1.3 Metabolic Assessments

A lipid panel (total cholesterol, low-density lipoprotein [LDL], high-density lipoprotein [HDL], and triglycerides) and hemoglobin A1c (HbA1c), fasting glucose, and fasting insulin will be assessed as part of clinical laboratory (see [Section 13.3](#)). Homeostatic model assessment of insulin resistance (HOMA-IR) will be calculated from fasting glucose and fasting insulin. Blood pressure (systolic and diastolic) will be assessed. Body weight, BMI, and waist circumference will be assessed as described in [Section 8.2.3](#).

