To evaluate the effect of tildacerfont in reducing ATCH in subjects with classic CAH over 12 weeks	3.13.	Absolute change from baseline in ATCH as determined via application of the delta theorem to the log scale analysis results after 12 weeks on double-blind, placebo-controlled treatment (Week 18)
To evaluate the effect of tildacerfont in reducing ATCH in subjects with classic CAH over 12 weeks	3.14.	Change from baseline in ATCH as assessed on the log scale after 12 weeks on double-blind, placebo-controlled treatment (Week 18)

Objective	Efficacy Analysis	
To characterize dose-exposure of Tildacerfont in CAH	3.15.	Estimate the within subject correlation of A4 and 17-OHP log scale values with tildacerfont plasma concentrations over time
Exploratory Efficacy (Optional Open-Label Extension Period) - Outside the Scope of this SAP		
To evaluate the effect of tildacerfont in reducing GC use to near-physiologic levels in subjects with classic CAH	4.1.	Proportion of subjects with GC dose $\leq$ 25 mg/day in HCe and A4 $\leq$ ULN at end of treatment (EOT)
To evaluate the percentage change in GC use in subjects with classic CAH	4.2.	Percent change from baseline in GC dose at EOT
To evaluate the effect of tildacerfont in reducing cardiovascular risk in subjects with classic CAH and at least one cardiovascular risk factor at baseline	4.3.	Proportion of subjects with improvement in at least one cardiovascular risk factor at EOT
To evaluate the effect of tildacerfont in eliminating TART(s) in male classic CAH subjects with TART(s) at baseline	4.4.	Proportion of male subjects without TART(s) at EOT who had TART(s) at baseline
Safety		
To evaluate the safety of tildacerfont in subjects with classic CAH	5.1.	AEs, SAEs

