**Table 6 Spruce 203 Cardiovascular Risk Factors by Sex**

Risk Factor	Assessment	Female Criterion	Male Criterion
Blood Pressure	Systolic Blood Pressure	$\geq 120$ mmHg; OR	$\geq 120$ mmHg; OR
	Diastolic Blood Pressure	$\geq 70$ mmHg	$\geq 70$ mmHg
Cholesterol	LDL Cholesterol	$\geq 110$ mg/dL; OR	$\geq 130$ mg/dL; OR
	Total Cholesterol	$\geq 170$ mg/dL	$\geq 200$ mg/dL
HOMA-IR	Fasting HOMA-IR	$\geq 2.5$	$\geq 2.5$
Waist Circumference	Waist Circumference	$\geq 88$ cm	$\geq 102$ cm
Body Mass Index	Body Mass Index	$\geq 30$ kg/m  ; OR at least one additional risk factor and BMI $\geq 27$ kg/m 	$\geq 30$ kg/m  ; OR at least one additional risk factor and BMI $\geq 27$ kg/m 

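### SAP 9.3.20 pairs the divisor 405 with glucose in mg/L instead of mg/dL, so its two alternative HOMA-IR formulas differ exactly tenfold

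*SAP*

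**What the plan says.** SAP 9.3.20 introduces the derivation with "HOMA-IR is calculated using the following equations" and gives two expressions joined by an 'or'. The first has "HOMA-IR = \frac{\text{glucose (mg/L)} * \text{insulin(mIU/L)}}{405" and the second has "glucose (mmol/L)} * \text{insulin(mIU/L)}}{22.5". Nothing says when to use which, so they are presented as equivalent.

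The protocol does not help. Section 8.1.3 says only that HOMA-IR "will be calculated from fasting glucose and fasting insulin", without a formula or units. SAP 9.3.20 is therefore the only derivation in either document, and SAP section 4 makes the SAP govern where the two disagree.

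The derived value is used in two explicit places in the SAP:

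- Section 11.3.2 lists it as a baseline characteristic in the insulin profile.
- Table 6 makes fasting HOMA-IR of 2.5 or more a cardiovascular risk factor for both sexes. The BMI row of the same table accepts a lower BMI limit of 27 kg/m² when there is "at least one additional risk factor and BMI" at that level.

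Protocol 9.4.5 also names HOMA-IR among the components of the extension-period cardiovascular endpoint. SAP Table 1 lists that endpoint (4.3) under a heading marked "Outside the Scope of this SAP".

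**The concern.** Two formulas offered as alternatives must return the same number for the same blood sample. These do not, because the glucose unit printed in the first one does not go with its divisor.

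HOMA-IR is compared with a fixed cut-off, so a scale error changes classification as well as presentation. If glucose were supplied in mg/L and the first formula followed to the letter, the baseline summary would be ten times too high and the 2.5 threshold would lose most of its power to discriminate. If some records were derived by one formula and some by the other, they would not be comparable. A derivation section exists so that a programmer can implement it without guessing, and here the text leaves the programmer to notice the conflict.

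**Working it through.** **Inputs**

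- Formula A (SAP 9.3.20): glucose in mg/L × insulin in mIU/L ÷ 405.
- Formula B (SAP 9.3.20): glucose in mmol/L × insulin in mIU/L ÷ 22.5.
- Glucose conversion (SAP Table 10, low limit for glucose): 3 mmol/L is paired with 54 mg/dL.
- Cut-off (SAP Table 6): HOMA-IR ≥ 2.5.

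**Step 1: reproduce the divisor.** Table 10 gives 54 ÷ 3 = 18 mg/dL per mmol/L, which is 180 mg/L per mmol/L. For A and B to agree, the divisor in A must be 22.5 times the number of glucose units per mmol/L.

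- mg/dL: 22.5 × 18 = 405. This reproduces the printed figure exactly.
- mg/L: 22.5 × 180 = 4050. This does not.

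Rounding of the conversion factor is not the explanation. An assumed factor of 18.016 gives 22.5 × 18.016 = 405.4 for mg/dL, still nowhere near 4050.

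**Step 2: size of the discrepancy.** For any sample, A ÷ B = (180 ÷ 405) × 22.5 = 10. The ratio does not depend on glucose or insulin.

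**Step 3: one worked sample (assumed values).** Take glucose of 5.0 mmol/L = 90 mg/dL = 900 mg/L, and insulin of 10 mIU/L.

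- mmol/L formula: 5.0 × 10 ÷ 22.5 = 2.22, below the cut-off.
- mg/dL over 405: 90 × 10 ÷ 405 = 2.22, below the cut-off.
- mg/L over 4050: 900 × 10 ÷ 4050 = 2.22, below the cut-off.
- mg/L over 405, as printed: 900 × 10 ÷ 405 = 22.2, above the cut-off.

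**Step 4: what the cut-off then means.** A printed value of 2.5 is a true value of 2.5 ÷ 10 = 0.25. The insulin at which a subject is flagged is 2.5 × 22.5 ÷ glucose (mmol/L) when correct, and one tenth of that as printed:

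| Assumed glucose (mmol/L) | Correct (mIU/L) | As printed with mg/L (mIU/L) |
|---|---|---|
| 3.9 | 14.4 | 1.44 |
| 5.0 | 11.25 | 1.125 |
| 7.0 | 8.0 | 0.80 |

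**Step 5: share of subjects flagged.** The documents give no insulin distribution, so this is an assumption shown over a range: lognormal insulin with median 4 to 12 mIU/L, log-SD 0.5 to 0.9, and glucose 4.5 or 5.0 mmol/L. The share is 1 − Φ[(ln threshold − ln median) ÷ log-SD].

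For example, with median 4, log-SD 0.9 and glucose 4.5, the thresholds are 12.5 (correct) and 1.25 (as printed), and the shares are 10.3% and 90.2%. Over the whole range, about 1% to 55% are flagged with the correct formula and about 90% to 100% under literal use of mg/L.

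**The case against.** The strongest reply is that this is a typographical slip beside a correct formula, and that it may never bite. Outside this formula the SAP gives glucose only in mmol/L or mg/dL, never mg/L. A programmer with mg/dL values would divide by 405 and get the right answer despite the label; one with mmol/L values would use the second formula and also be right. The error needs glucose to be supplied in, or converted to, mg/L. Protocol 8.2.5 sends study-required clinical laboratory tests to a central laboratory, which makes a mixture of units less likely. All of this stands, and it is why the point is minor.

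A reader might go further and infer that nearly every subject will be classed as insulin resistant. The documents do not support that as a plain statement. It requires literal mg/L input, and it rests on an insulin distribution that they do not give.

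A reader might also infer that the BMI ≥ 27 rule becomes automatic. Table 6 already lets a subject meet that rule through systolic pressure of 120 mmHg or more, diastolic pressure of 70 mmHg or more, cholesterol or waist circumference. A false HOMA-IR flag would be one more route, and its added effect cannot be sized from the documents.

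Finally, a reader might infer that subjects could hardly ever leave the risk category. That describes endpoint 4.3, which this SAP does not analyse.

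The equation was read from a PDF by a program, so the missing letter could be a reading error. Table 6 and Table 10 show mg/dL read correctly, which makes this unlikely, but the sponsor should check the source file.

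**Conclusion.** The point holds as a unit error in a derivation rule. The factor of 10 is exact and follows from the SAP's own figures. It needs no assumption beyond the two formulas being meant as equivalent.

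The consequence is conditional. Only if the first formula is applied to glucose in mg/L would the baseline HOMA-IR summary be inflated tenfold and the 2.5 cut-off act as 0.25. The statement that most subjects would then be flagged rests on the assumed insulin range above.

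The reach is limited. No primary, secondary or numbered exploratory analysis for Parts A to C (1.1 to 3.15) is defined on HOMA-IR, and the additional metabolic summaries in SAP 13.5.10.4 do not list it. The A4 and 17-OHP conclusions are unaffected. Severity is minor, but the text is wrong as written and should not pass unchanged into the extension SAP, where the cardiovascular endpoint would depend on it.

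**What to change.** In SAP 9.3.20, change the glucose unit in the first formula from mg/L to mg/dL, leaving 405 as it is. Alternatively, delete that formula and keep only the mmol/L version with 22.5. Carry the same correction into the separate extension SAP, where endpoint 4.3 will use the Table 6 definition. If HOMA-IR has already been programmed, confirm which glucose unit the code reads.

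The cost is one unit label in the SAP and a short check of the derivation code. No data collection, sample size or efficacy analysis changes.

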#### **9.3.21 Testicular Adrenal Rest Tumor Volume**

For each TART assessment, the total number of TARTs will be captured as well as the size (lesion volume) of each TART individually. The total lesion volume of all detectable TARTs per subject will be calculated and will be compared against baseline total lesion volume.

#### **9.3.22 Cardiovascular Risk Factors**

Cardiovascular risk factors are derived from the metabolic risk factors. There are seven assessments spanning eight criteria that fit one of five cardiovascular risk factors.

**Table 6 Spruce 203 Cardiovascular Risk Factors by Sex**

Risk Factor	Assessment	Female Criterion	Male Criterion
Blood Pressure	Systolic Blood Pressure	$\geq 120$ mmHg; OR	$\geq 120$ mmHg; OR
	Diastolic Blood Pressure	$\geq 70$ mmHg	$\geq 70$ mmHg
Cholesterol	LDL Cholesterol	$\geq 110$ mg/dL; OR	$\geq 130$ mg/dL; OR
	Total Cholesterol	$\geq 170$ mg/dL	$\geq 200$ mg/dL
HOMA-IR	Fasting HOMA-IR	$\geq 2.5$	$\geq 2.5$
Waist Circumference	Waist Circumference	$\geq 88$ cm	$\geq 102$ cm
Body Mass Index	Body Mass Index	$\geq 30$ kg/m  ; OR at least one additional risk factor and BMI $\geq 27$ kg/m 	$\geq 30$ kg/m  ; OR at least one additional risk factor and BMI $\geq 27$ kg/m 

### **9.3.23 Study Drug Exposure Variables**

#### **9.3.23.1 Study Drug**

Study drug is defined as either tildacerfont or placebo.

#### **9.3.23.2 Study Treatment**

Study treatment is defined more broadly as study drug or HC for stress dosing provided by the Sponsor.

#### **9.3.23.3 Study Drug Exposure Duration (days)**

The duration (days) of study drug exposure is derived from the first dose date and the last dose date of a given period of time. Specifically, the duration (days) is calculated as (LASTDAY - FIRSTDAY + 1 day), where LASTDAY is the date of last dose, and FIRSTDAY is the date of first dose. If it becomes known that a patient has multiple consecutive missed doses, an adjustment to the calculation of exposure duration may be made.

The date of the first dose is captured by the CRF question, “Date first dose of study drug from this supply was taken by the subject?” For each treatment period, the first dose date is specifically collected from the following protocol-specified dispensations:

**Table 7 First Dose of Treatment Period by Dispensation**

Treatment Period	Dispensation Visit	Subsequent Visit
Run-in	Week 0	Week 4
Part A	Week 6	Week 10
Part B	Week 18	Week 24
Part C	Week 30	Week 38
Optional Open-Label Extension Period	Week 76	Week 88

In the absence of a scheduled dispensation, the first dose of study drug taken from an unscheduled dispensation that is windowed to the corresponding visit may be used. Otherwise, the date of the first dose of study drug from subsequent dispensation visit may be used.

The last dose date for a treatment period can be the last dose date of study drug treatment if the subject did not continue to the following treatment period, or one day prior to the date of the first dose date of the following treatment period.

#### **9.3.23.4 Total Tildacerfont Dose (mg) Taken**

Total tildacerfont dosage (mg) is defined as the dosage of tildacerfont taken over a specific study period  $i$  (where subject is receiving a constant dose), calculated as follows:

$Total Tildacerfont Dose_i$

$$= ((\#Dispensed - \#Returned - \#Lost\ or\ Destroyed) \times Tablet\ Strength)_i$$

and total tildacerfont dose over the entire study period is calculated as:

$$Total Tildacerfont Dose = \sum_{i=1}^k (Total Tildacerfont Dose)_i$$

where

$\Sigma$  represents the summation operator and the value in parentheses is summed over the sequence  $i = 1$  to  $k$ , where  $k$  = number of time intervals subject is intended to receive study drug, and tablet strength

Tablet strength is 0 mg per tablet if placebo or 50 mg tildacerfont per tablet if active drug.

### 9.3.23.5 Study Drug Compliance per Treatment Period

Study drug compliance is defined as the percentage of study drug actually taken compared to what was expected based on the randomized or titrated dose for time period  $i$  (where subject is receiving a constant dose). Using the drug accountability data, study drug compliance is calculated as follows:

$$\%Compliance_i = 100 \times \left( \frac{\# Dispensed - \# Returned - \# Lost or Destroyed}{\# Expected tablets to be taken} \right)_i$$

and total % compliance over a treatment period is calculated as:

$$\%Compliance = 100 \times \left( \frac{\sum_{i=1}^k (\# Dispensed - \# Returned - \# Lost or Destroyed)_i}{\sum_{i=1}^k (\# Expected tablets to be taken)_i} \right)$$

where

$\Sigma$  represents the summation operator and the value in parentheses is summed over the sequence  $i = 1$  to  $k$ , where

$k$  = number of time intervals subject is receiving a constant dose. Possible constant dose levels are placebo, 50 mg QD tildacerfont, 100 mg QD tildacerfont, or 200 mg QD tildacerfont. At 50 mg QD tildacerfont dose level, 1 active tablet and 3 placebo tablets are taken per administration (i.e., 4 tablets per day); at 100 mg QD tildacerfont dose level, 2 active tablets and 2 placebo tablets are to be taken per administration (i.e., 4 tablets per day); at 200 mg QD tildacerfont, 4 active tablets are to be taken per administration (i.e., 4 tablets per day).

The expected number of tablets to be taken is the number of expected tablets per day (4 tablets) multiplied by the number of days in time period  $i$ .

### 9.3.23.6 Mean Daily Tildacerfont Dose (mg/day)

Mean Daily tildacerfont Dose (mg/day) is calculated as Total Tildacerfont Dose (mg) (Section 9.3.23.4) divided by Treatment Duration (days) for each treatment period (Part A, Part B, and Part C).

### 9.3.23.7 Diary Compliance

Subjects will fill out the daily GC and study drug diary through the Run-in Period and Part A. For all diary compliance, missing entries are counted as non-compliance. Daily study drug diary

compliance is calculated as the total count of number of 'Yes' responses to taking study drug as directed divided by (LASTDAY – FIRSTDAY+ 1 day), where LASTDAY is the date of last dose, and FIRSTDAY is the date of first dose.

Daily food diary compliance is calculated as the total count of number of 'Yes', with evening meal' responses to taking study drug with an evening meal, divided by (LASTDAY – FIRSTDAY+ 1 day).

Daily GC diary compliance is calculated as the total count of number of 'Yes' or 'Took Stress Dosing' responses to taking GC as directed and number of stress dosing days, divided by (LASTDAY – FIRSTDAY+ 1 day).

Weekly diary compliance is calculated as the total count of number of 'Yes', 'Yes, with evening meal' and/or 'Took Stress Dosing' responses to taking study drug as directed within the duration {Study Day (7n+1) to Study Day (7[n+1])}, divided by 7. Where n has values {0, 1, 2, ..., 18}. Missing entries are counted as non-compliance.

Aggregate diary compliance is calculated as (study drug compliance + food compliance + GC diary compliance) divided by 3.

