## 5 STUDY DESIGN

This is a multi-center, randomized, double-blind, placebo-controlled, dose-ranging clinical study with a 3-part Treatment Period and an optional Open-Label Extension Period. The 3-part Treatment Period will evaluate the efficacy and safety of up to 70 weeks of treatment with tildacerfont in adult subjects with classic CAH who have elevated biomarkers at baseline. At least 72 adult subjects will be randomized into the Treatment Period of the study.

A 6-week, single-blind, placebo Run-in Period, will assess subjects for adherence to their existing GC therapy and daily ingestion of placebo with food. Upon completion of a 6-week single-blind, placebo Run-in Period, subjects who meet all eligibility criteria will be randomized into the Treatment Period. Subjects will be randomized in a 1:1:1:1 ratio to receive either tildacerfont at a dose of 50 mg (once daily) QD, 100 mg QD, and 200 mg QD or matching placebo along the randomization stratum (Week 4 A4  $\leq$  4  $\times$  upper limit of normal [ULN] versus Week 4 A4  $>$  4  $\times$  ULN). The first 12 weeks of the treatment period constitute the randomized, double blind, placebo-controlled, dose finding treatment period (Part A).

Following Part A, all subjects will receive tildacerfont for duration of 12 weeks (Part B) with opportunities to up-titrate their tildacerfont dose up to 200 mg QD based on treatment response. Placebo subjects will receive the 100 mg tildacerfont QD dose at the beginning of Part B. Part B will have possible dose escalations at Week 18 and Week 24 for eligible subjects not meeting androstenedione (A4) response criteria as an assessment of dose titration for non-responders (A4  $>$  upper limit of normal [ULN]).

Part C is a 46-week treatment period in which all subjects are escalated to receive 200 mg tildacerfont QD at Week 30, with opportunities for glucocorticoid (GC) reduction for eligible subjects (subjects meeting A4  $\leq$  ULN).

Subjects continuing into the optional Open-Label Extension Period will receive 200 mg tildacerfont QD for up to 240 weeks of treatment, with opportunities for GC adjustment for eligible subjects at each visit. Upon completion of the Open-Label Extension Period or completion of Treatment Period Part C for those subjects who do not continue into the Open-Label Extension Period, subjects will return to the clinic within 30 days following their last dose for a Follow-up visit.

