### **8.3 Per-Protocol Analysis Set**

The Per-Protocol (PP) Analysis Set for Part A of the Treatment Period will include all eligible subjects who have no major protocol deviations that would affect the analysis of efficacy data. The PP Analysis Set may be used for supportive secondary analyses of the primary and secondary efficacy endpoints.

Major protocol deviations that would affect the analysis of efficacy data are listed as the following, but not limited to:

- Randomization error
- Subject did not meet efficacy-based inclusion criteria (elevated biomarkers)
- Subject met efficacy-based exclusion criteria (use of dexamethasone, night-shift worker), without waiver
- Subject's aggregate drug compliance was < 80% over the Treatment Period

Additional deviations will be identified prior to database lock and updated in this section.

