### 9.3.26.3 Stress Event

A stress event is defined as an entry in the diary indicating a stress dose was taken. Consecutive days of stress dosing are counted as a single stress event.

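### Read literally, the SAP's GC diary compliance formula counts each stress-dosing day twice, overstating a descriptive adherence measure

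*SAP*

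**What the plan says.** SAP 9.3.23.7 builds the numerator of GC diary compliance in one sentence. It begins "Daily GC diary compliance is calculated as the total count of number of 'Yes' or 'Took Stress Dosing" and continues "responses to taking GC as directed and number of stress dosing days". The denominator is LASTDAY minus FIRSTDAY plus one day, "where LASTDAY is the date of last dose, and FIRSTDAY is the date of first dose".

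The same section states: "For all diary compliance, missing entries are counted as non-compliance". It gives neither a cap at 100% nor a rule for removing duplicate days.

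SAP 9.3.26.3 takes stress events from the same source: "A stress event is defined as an entry in the diary indicating a stress dose was taken".

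The result is used in two places. SAP 12.2 plans a summary of overall GC diary compliance and cites this definition. SAP 9.3.23.7 also averages it with two other measures: "Aggregate diary compliance is calculated as (study drug compliance + food compliance + GC diary compliance) divided by 3".

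**The concern.** A day on which the subject took a stress dose is already one 'Took Stress Dosing' response. Adding the number of stress-dosing days counts it again, while the denominator still counts it once. The measure then rises with days of illness, and a stress day can cancel a day on which GC was missed or the diary left blank, although the SAP says blank entries count against the subject.

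What is at stake is the description of background GC adherence by arm. Protocol 4.2 recognises that a change in GC adherence can move the biomarkers independently of tildacerfont, and SAP 13.3.1 lists lack of GC compliance among the intercurrent events. A reader would use the SAP 12.2 summary to judge whether GC was taken comparably across arms. If stress dosing differs between arms, the written formula distorts that comparison.

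**Working it through.** The documents give no compliance figure to reproduce, so the check is arithmetic on the written formula.

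**Inputs**
- D = diary days. For Part A, D = 84, from "The first 12 weeks of the treatment period constitute the randomized" treatment period in SAP 5 (12 × 7). For the Run-in, D = 42 (6 × 7). Both assume that first to last dose spans the full period.
- S = days answered 'Took Stress Dosing'; M = days answered 'No' or left blank; Y = D − S − M = days answered 'Yes'. S and M are assumptions, because the documents do not forecast them. The only guide is Protocol Table 2, where home stress dosing usually lasts 2 to 3 days.

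**Formulas**
- As written: 100 × (Y + S + S)/D = 100 × (D − M + S)/D
- Each day once: 100 × (Y + S)/D = 100 × (D − M)/D
- Overstatement: 100 × S/D points
- The written form exceeds 100% exactly when S > M. With S = 0 the two forms agree.

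**Results**

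| D | S | M | As written | Each day once |
|---|---|---|---|---|
| 84 | 0 | 5 | 79/84 = 94.0% | 79/84 = 94.0% |
| 84 | 3 | 0 | 87/84 = 103.6% | 84/84 = 100.0% |
| 84 | 3 | 3 | 84/84 = 100.0% | 81/84 = 96.4% |
| 84 | 7 | 17 | 74/84 = 88.1% | 67/84 = 79.8% |
| 42 | 3 | 0 | 45/42 = 107.1% | 42/42 = 100.0% |

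In Part A each stress day adds 100/84 = 1.2 points, so one episode of 2 to 3 days adds 2.4 to 3.6 points.

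**Aggregate diary compliance.** GC is one of three equally weighted parts, so the overstatement is 100 × S/(3D). In Part A that is 100/252 = 0.4 points per stress day: 1.2 points for S = 3 and 2.8 points for S = 7.

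**Comparison within the section.** The weekly formula in SAP 9.3.23.7 also accepts 'Took Stress Dosing' responses but has no separate stress-day term. The study drug and food formulas count each day at most once. Only the daily GC formula has the extra term, which suggests that a single count was intended.

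**The case against.** The phrase may be loose drafting that restates which days qualify, not a second addend. The weekly formula supports that intention. It might also be meant to catch stress days recorded elsewhere: Protocol 8.3.8 has stress-dosing start and stop dates collected in the diary, and Protocol 6.5.1.5 has stress doses entered in the EDC. The diary form is not in the documents, so complete overlap between the two terms is inferred, though SAP 9.3.26.3 supports it. These points bear on intent. The text still reads as a sum, and a programmer following it would add the term. If it is a restatement, deleting it loses nothing. If it draws on another record, the days still overlap unless duplicates are removed.

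The limits on impact stand. No model in the SAP uses diary compliance. SAP 13.3.1 keeps the data whatever the GC compliance. The mITT set turns on a change in background GC. Missed days are not wholly hidden either, because SAP 12.1 lists every diary entry and values above 100% would be conspicuous.

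It is also fair to say that the corrected formula still scores a stress day as compliant. It does so once, which is the SAP's own choice and fits Protocol 6.5.1.5, where the stress dose replaces the usual daily dose.

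A reader might infer that the error reaches the per-protocol set, because SAP 8.3 excludes subjects whose "aggregate drug compliance was < 80% over the Treatment Period" and the only measure that the SAP otherwise calls aggregate is the diary one. The documents do not support that step:
- SAP 8.3 refers to drug compliance, not diary compliance.
- SAP 9.3.23.5 defines a total study drug compliance over a treatment period from tablet counts, and SAP 12.1 names drug accountability as the source.
- The parent rule in Protocol 9.3 says only drug compliance.
- The adherence diary stops at Week 18, which fits poorly with a criterion over the Treatment Period.

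**Conclusion.** The formula is wrong as written. Under its literal reading, GC diary compliance is overstated by S/D, can exceed 100%, and lets each stress day offset one missed GC day. The size depends on assumed day counts: 2.4 to 3.6 points in Part A for one typical episode, and 8.3 points (7/84) in the more extreme case of 7 stress days. Aggregate diary compliance moves by a third of that.

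The effect is confined to the descriptive GC summary in SAP 12.2 and to aggregate diary compliance. That the illustrative 79.8% and 88.1% fall on either side of 80% has no consequence, since the documents apply no 80% cut-off to this measure. Run-in exclusion (Protocol 5.1.2, criterion 5) does use 80%, but bases it on drug accountability. The per-protocol criterion is most naturally the accountability-based measure too. This is a minor correction that leaves the efficacy conclusions untouched.

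**What to change.** In SAP 9.3.23.7, delete the words that add the number of stress-dosing days. The definition becomes: GC diary compliance = (days answered 'Yes' or 'Took Stress Dosing') / (LASTDAY − FIRSTDAY + 1), with each calendar day counted at most once. If stress days recorded outside the diary response are meant to count, say so and state that a day found in both records counts once.

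The cost is one phrase in the SAP and the matching line in the derived-variable specification. No new data are needed and no analysis set changes.
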